2 INTRODUCTION

This statistical analysis plan (SAP) addresses the planned analyses for the OPTION trial based on the approved protocol version E. The primary efficacy endpoint analysis will use time-to-event Kaplan-Meier estimates and Greenwood formula for variance to assess noninferiority of the Device vs the Control at a specific timepoint. The primary safety endpoint analysis will use log-rank statistics to assess superiority of Device vs Control over time.

3 ENDPOINT ANALYSES

3.1 Primary Efficacy Endpoint

The primary efficacy endpoint is the occurrence of stroke (including ischemic and/or hemorrhagic), all cause death, and systemic embolism at 36 months. This endpoint is defined as the Kaplan Meier estimate of time to first occurrence of stroke (including ischemic and/or hemorrhagic), all cause death, or systemic embolism at 36 months and will be tested for non-inferiority of WATCHMAN to control.

3.1.1 Hypotheses

The objective of the primary efficacy endpoint analysis is to test the null hypothesis that the difference in cumulative incidence between the Device and Control groups is greater than a prespecified noninferiority margin δ . The null hypothesis will be tested vs. the one-sided alternative hypothesis that the difference in cumulative incidence is less than a noninferiority margin δ .

 $H_0: S_1(t) \ge S_0(t) + \delta$

 H_a : $S_1(t) < S_0(t) + \delta$,

where $S_1(t)$ and $S_0(t)$ are the Kaplan Meier estimates for the cumulative incidence of stroke (including ischemic and/or hemorrhagic), all-cause death, and systemic embolism at 36 months for the Device and Control groups, respectively.

3.1.2 Sample Size for the Primary Efficacy Endpoint

The power and sample size were calculated employing Farrington Manning methods for non-inferiority using SAS version 9.4. The assumptions and parameters pertaining to this design are as follows:

- Power = 85.9%
- Alpha = 0.025 (one-sided)
- Expected Device and Control group performance: cumulative incidence rate of 10% at 36 months in both groups
- A noninferiority margin $\delta = 5\%$
- Attrition: cumulative attrition rate of 15% in the Device Group and in the Control group at 36 months.

The expected cumulative incidence of 10% at 36 months in the Device group was derived from historical event rates from the PROTECT AF, CAP, PREVAIL, and CAP2 studies. WATCHMAN subjects with previous ablations from these studies experienced a 14.4% event at

3 years. The cumulative incidence is expected to be lower in the OPTION study due to enhanced implant experience over time, device improvements, and a decreased baseline risk profile for subjects enrolled in the OPTION study. The expected cumulative incidence in the Control arm is expected to be equal to that of the Device arm.

The non-inferiority margin of 5% represents a relative risk of 1.5.

Given the above assumptions, 1360 subjects will be required. In order to account for up to 15% expected rate of attrition which includes subjects randomized but not treated and subjects withdrawn or lost-to-follow-up through 36 months, a total of 1600 (1360/(1-0.15)) subjects need to be enrolled.

A sample size of 1600 subjects provides 85.9% power for the Primary Effectiveness Endpoint analysis. Therefore, a maximum sample size of 1600 is determined.

In addition, the power and sample sizes have been re-evaluated for the non-inferiority testing settings that would match the method described to perform the hypothesis analysis, namely, differences in the Kaplan-Meier event rates of the respective endpoints using the Greenwood formula.

The operating characteristics of the statistical test for the primary effective endpoint, and the secondary safety endpoint, are calculated by simulating 10,000 trials, for each endpoint, for a given sample size using custom-written code in SAS. The results are consistent with the sample size calculation performed using a parametric formula, namely the Farrington-Manning method above. The table below presents the simulation results for primary efficacy endpoint.

Power and type I error of the Simulation for Primary Effective Endpoint

Method	Farrington-Manning	Simulation
Power	85.9%	89.3%
Alpha (Type I error)	0.025	0.024

3.1.3 Statistical Methods for the Primary Efficacy Endpoint

The primary efficacy endpoint event rate from the WATCHMAN FLX Device and Control arms, $S_1(t)$ and $S_0(t)$, respectively, will be estimated by the Kaplan Meier method. The timepoint of 36 months is defined as the 1095^{th} day post-randomization. The 97.5% one-sided upper bound of confidence limit of the difference between WATCHMAN FLX and Control rates will be calculated using Greenwood formula for the variance of the Kaplan Meier estimates. The objective is met if this confidence limit is less than the predefined noninferiority margin of 5%.

3.1.4 Superiority Test for the Primary Efficacy Endpoint

If the non-inferiority hypothesis objective is met and the observed event rate favors the Device arm, i.e., $S_1(t) < S_0(t)$, a superiority test will be subsequently performed and a one-sided p-value of 0.025 will be considered significant. No multiplicity adjustment is needed¹.

¹ B Logan and A Tamhane, Superiority Inferences on Individual Endpoints Following Noninferiority Testing in Clinical Trials, Biometrical Journal 50 (2008) 5.

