13.1.1.3. Statistical Methods

The primary efficacy endpoint event rate from the WATCHMAN FLX Device and Control arms, S₁(t) and S₀(t), respectively, will be estimated by the Kaplan Meier method. The time point of 36 months is defined as the 1095th day post-randomization. The 97.5% one-sided upper bound of confidence limit of the difference between WATCHMAN FLX and Control rates will be calculated using Greenwood formula for the variance of the Kaplan Meier estimates. The objective is met if this confidence limit is less than the predefined noninferiority margin of 5%.

If the non-inferiority hypothesis objective is met, a superiority test will be subsequently performed and a one-sided p-value of 0.025 will be considered significant.

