3.3.4 Superiority Test for the Secondary Endpoint

If the non-inferiority hypothesis objective is met and the observed event rate favors the device arm, i.e., $S_1(t) < S_0(t)$, a superiority test will be subsequently performed and a one-sided p-value of 0.025 will be considered significant. No multiplicity adjustment is needed.¹

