3.3.5 Multiplicity Consideration

The strategy to avoid the multiplicity issue for the additional tests is to have a hierarchical order for the hypothesis tests and the testing significance level [1] for all hypothesis testing is one-sided alpha 0.025. The hypothesis testing will follow the order below.

- 1. Superiority testing of the primary safety endpoint and non-inferiority testing of the primary efficacy endpoint,
- 2. Non-inferiority testing of the secondary endpoint,
- 3. Superiority testing of the secondary endpoint and
- 4. Superiority testing of the primary efficacy endpoint.

The study is successful if Superiority testing of the primary safety endpoint and non-inferiority testing of the primary efficacy endpoint are met.

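### SAP 3.1.4 and 3.3.4 gate each superiority test only on its own non-inferiority result, SAP 3.3.5 sets a fixed order, and nothing says which governs

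*SAP*

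**What the plan says.** **Rule in the endpoint sections.** SAP 3.1.4 opens the efficacy superiority test with "If the non-inferiority hypothesis objective is met and the observed event rate favors the Device arm". It then sets the level: "a superiority test will be subsequently performed and a one-sided p-value of 0.025 will be considered significant. No multiplicity adjustment is needed". A footnote cites a methods paper on superiority inference after non-inferiority testing. SAP 3.3.4 repeats the rule for the secondary endpoint, again ending "No multiplicity adjustment is needed". Protocol 13.1.1.3 has the same gate without the condition on the estimate: "If the non-inferiority hypothesis objective is met, a superiority test will be subsequently performed", at one-sided 0.025. Protocol 13.1.3.3 does the same for the secondary endpoint.

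**Rule in the multiplicity section.** SAP 3.3.5 says that the level "for all hypothesis testing is one-sided alpha 0.025. The hypothesis testing will follow the order below". The order is:

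- "1. Superiority testing of the primary safety endpoint and non-inferiority testing of the primary efficacy endpoint"
- "2. Non-inferiority testing of the secondary endpoint"
- third, secondary superiority
- "4. Superiority testing of the primary efficacy endpoint"

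It defines trial success by the first step alone.

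**What is silent.** SAP 3.1.4 and 3.3.4 do not refer to 3.3.5, and 3.3.5 does not say that it overrides them. SAP 4.4, the section on type I error, covers only the two co-primary tests. Protocol section 13 contains no testing order.

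**The concern.** The two rules give different answers whenever efficacy superiority reaches one-sided p < 0.025 but the safety test or either secondary test fails. Suppose efficacy superiority gives p = 0.02 and secondary superiority is not met. SAP 3.1.4 calls the efficacy result significant; SAP 3.3.5 never reaches the test.

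The result in dispute would be a confirmatory claim that the device reduces stroke, death or systemic embolism. Both rules are pre-specified, so either could be quoted in its support. Moving from non-inferiority to superiority within one endpoint costs no alpha. That argument does not cover a second endpoint tested at the same full level, which is what the fixed order in 3.3.5 handles.

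**Working it through.** **Inputs.** One-sided 0.025 per test (SAP 3.1.4, 3.3.4, 3.3.5). Power of the step-1 tests: 89.3% for efficacy non-inferiority (SAP 3.1.2, simulated) and 86.4% for safety superiority (SAP 3.2.2). Planned rates are equal between arms: 10% for efficacy (SAP 3.1.2) and 11% for the secondary endpoint (SAP 3.3.2). The documents give no correlation between endpoints, so values from 0 to 0.5 are assumed. SAP 3.1.4 names no superiority statistic; I assume the same Kaplan-Meier/Greenwood statistic, so that superiority at 0.025 implies non-inferiority.

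**The plan's figures.** The Farrington-Manning powers reproduce: 85.9% with 1360 subjects for efficacy and 84.3% with 1280 for the secondary endpoint. Re-simulating the Kaplan-Meier test at 1600 gives 88.4% and 88.6%, against the stated 89.3% and 88.9%. The safety power is taken as stated.

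**Fixed order (3.3.5).** Suppose both the efficacy superiority null and a secondary null are true. A false efficacy claim at step 4 can then occur only after a false secondary claim, so it adds nothing to the error.

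- Step 1 certain to pass: 0.025, the maximum.
- Step 1 at design power, independent tests: 0.893 × 0.864 × 0.025 = 0.0193.

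**Efficacy superiority released by 3.1.4.** It becomes a second chain at 0.025 beside the secondary endpoint.

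- Step 1 certain to pass, independent tests: 1 − (1 − 0.025)² = 0.0494. The Bonferroni bound is 0.025 + 0.025 = 0.050.
- Step 1 at design power, gating only the secondary endpoint: 0.025 + 0.0193 − 0.025 × (0.864 × 0.025) = 0.0437.
- Step 1 at design power, gating both chains: 0.864 × 0.025 + 0.0193 − 0.0005 = 0.0403.

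A simulation of 4 million trials gave the same values to within rounding. Adding correlation:

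| Assumption | One-sided family-wise error |
|---|---|
| Step 1 certain, correlation 0 | 4.94% |
| Step 1 certain, correlation 0.1 / 0.2 / 0.3 / 0.5 | 4.90% / 4.84% / 4.76% / 4.54% |
| Design power, correlation 0, secondary gated only / both gated | 4.4% / 4.0% |
| Design power, correlation 0.3, both readings | about 4.6% |
| 3.3.5 order, maximum | 2.5% |
| 3.3.5 order, design power, correlation 0 / 0.3 | 1.9% / 2.4% |

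**How often the rules would disagree.** With equal 11% rates, secondary superiority is met with probability 0.025. Given a nominally significant efficacy superiority result, and assuming independence, the 3.3.5 order allows the claim with probability 0.864 × 0.025 = 0.0216. The rules then disagree in about 98% of such cases. If the device truly lowers major bleeding, or the endpoints are positively correlated, the share is smaller.

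**The case against.** The strongest reply is that the sections can be read together. SAP 3.1.4 gives necessary conditions and a level; it does not say that the test follows at once. SAP 3.3.5 is the section on multiplicity, covers every hypothesis test, and uses the same level. It can fairly be read as governing. That reading stands as reasonable and may be what was intended. It remains an inference, because 3.1.4 addresses this exact test and says no adjustment is needed.

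Other parts of the reply stand in full:

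- The no-adjustment sentence is correct for switching within one endpoint.
- Protocol section 13 calls itself an overview and defers details to the SAP, so the missing order there is not a defect in itself.
- Independence is doubtful. Death and hemorrhagic stroke count for efficacy (Protocol 7.1), and fatal or intracranial bleeding counts as ISTH major bleeding (Protocol 29.2.3.2).
- Efficacy superiority was not what the trial was sized for, given equal planned rates.

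A reader might also infer that the SAP states a 2.5% family-wise rate and then breaches it. It does not: 0.025 is the level of each test, and the 2.5% bound follows from the fixed order. Nor do the documents support treating three parallel tests, 1 − 0.975³ = 7.3%, as the size of the problem. That figure also takes the safety null as true and counts a safety rejection alone as a claim, whereas SAP 3.3.5 and 4.4 treat the co-primaries as one joint requirement.

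**Conclusion.** The point holds as an unresolved conflict between the endpoint sections and the multiplicity section. If 3.1.4 were followed instead of 3.3.5, the one-sided family-wise error for claims beyond the co-primaries would be up to about 4.9%, against at most 2.5% under the fixed order. The 4.9% is close to a ceiling: it assumes independent tests, both nulls true and step 1 almost sure to pass. Across the gate powers and assumed correlations tabulated above, the range is about 4.0% to 4.9%.

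A reader might infer that the trial's success criterion is compromised. It is not: success depends only on safety superiority and efficacy non-inferiority, which both rules leave untouched. Nor does 4.9% satisfy the below-5% statement in SAP 4.4, which is a two-sided level for the co-primaries only. The matter should be settled before the analysis, but it does not threaten the primary conclusion.

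**What to change.** In SAP 3.1.4 and 3.3.4, add that the superiority test is *tested only if all earlier steps in Section 3.3.5 have been met*, and state that 3.3.5 governs. Keep the no-adjustment sentence, but limit it to the switch from non-inferiority to superiority within the same endpoint.

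An SAP edit is enough. Protocol 13.1.1.3 and 13.1.3.3 can be aligned at a future amendment; under Protocol 18.3 an amendment needs ethics approval, which this point alone does not warrant.

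The change needs no extra subjects or data. Its downside is that efficacy superiority can be claimed less often than under 3.1.4 alone, because secondary superiority must be shown first. If 3.3.5 was always meant to govern, nothing is lost.

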3.2 Primary Safety Endpoint

The primary safety endpoint is non-procedural bleeding through 36 months (ISTH major bleeding and clinically relevant non-major bleeding). This endpoint is defined as the Kaplan Meier estimate of time to first occurrence of non-procedural ISTH major bleeding or clinically relevant non-major bleeding through 36-months. Non-procedural events are those occurring after 3 days, calculated from implant or attempted implant date for Device patients and from date of randomization for Control patients. This endpoint will be tested for superiority of WATCHMAN vs Control.

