10.2.2. Randomized

Prior to randomization, the planned ablation procedure type, concomitant or sequential, must be specified. A randomized subject is a subject who signs informed consent and is randomized. Subjects must not be randomized unless they have a valid and signed informed consent and meet all inclusion and no exclusion criteria.

For subjects in the sequential group, randomization can only occur between 90 and 180 days following the most recent AF ablation procedure. Subjects who are planning to have a concomitant procedure must be randomized within 10 days prior to the planned ablation procedure. All subjects (concomitant or sequential) randomized to the Device Group are required to undergo WATCHMAN FLX Device implant within 10 calendar days of randomization. Both groups are followed in accordance with the follow-up schedule. All applicable case report forms per the protocol must be completed. The original signed informed consent and any relevant documentation must be maintained in the site's subject file.

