10.2.3.1. Intent

A Randomized subject in the Device Group that does not have an implant attempt (i.e., WATCHMAN Access Sheath is never inserted into the body) will be classified as an "Intent" subject. The reason for the Intent will be collected in the database. Intent subjects count towards the enrollment ceiling and will be used for analyses of the endpoints according to intention-to -treat principles. Intent subjects will be followed according to the follow-up schedule with the exception of the follow-up LAA imaging. Intent subjects are not required to have the 3-month and 12-month follow-up LAA imaging. Intent subjects are not required to follow the Device Group medication requirements, but antiplatelet, NSAIDs, anticoagulant, and antiarrhythmic medications must be captured in the medication logs. All applicable case report forms per the protocol must be completed. The original signed informed consent and any relevant documentation must be maintained in the site's subject file.

Confidential Form/Template 90702637_Rev/Ver AP OPTION Protocol, document # 92320955, Rev E Page 44 of 102

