13.1.2. Primary Safety Endpoint

The Primary Safety Endpoint is Kaplan Meier estimate of time to first occurrence of non-procedural bleeding (ISTH major bleeding and clinically relevant non-major bleeding) through 36 months. Non-procedural events are those occurring after 3 days.

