3.2.3 Statistical Methods for the Primary Safety Endpoint

All subjects in the randomized cohort will be included in the analysis. A log-rank test will be performed including all subjects in database at the time of analysis post 36 months. The objective is met if the p-value of the log-rank test is less than 0.05.

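### SAP 3.2 gives the 3-day bleeding rule no start date for Device subjects without an implant attempt and, read literally, leaves out Device bleeds before implant

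*SAP*

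**What the plan says.** SAP 3.2 sets the start of the 3-day rule by arm. For Device it reads: "Non-procedural events are those occurring after 3 days, calculated from implant or attempted implant date for Device patients". The other arm has a different start: "and from date of randomization for Control patients". Protocol 13.1.2 has the same 3 days but no start date: "Non-procedural events are those occurring after 3 days".

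Protocol 10.2.2 allows a gap before the procedure. All subjects "randomized to the Device Group are required to undergo WATCHMAN FLX Device implant within 10 calendar days of randomization".

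Protocol 10.2.3.1 defines an Intent subject: "A Randomized subject in the Device Group that does not have an implant attempt". It keeps these subjects in: "Intent subjects count towards the enrollment ceiling and will be used for analyses of the endpoints", on intention-to-treat principles. Protocol 13.2.1 makes intention to treat primary for every primary and secondary endpoint. SAP 3.2.3 agrees for safety: "All subjects in the randomized cohort will be included in the analysis".

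SAP 4.1 differs. It puts the primary safety analysis on the treated-as-assigned set. On the Device side that set holds only successful implants, with follow-up starting on the procedure day. SAP 7.3 counts days from randomization.

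**The concern.** The rule is meant to remove bleeding caused by the implant procedure. As worded, it admits a Device bleed only if it falls more than 3 days after a procedure. That is not the same thing. A bleed before the procedure, or in someone who never has one, cannot meet the condition, although no procedure caused it. In Control the clock starts at randomization, so no comparable bleed is lost.

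Any loss is therefore confined to Device. It bears on a superiority test for bleeding that SAP 3.3.5 requires for trial success, and SAP 4.4 states that its type I error is held.

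**Working it through.** **Three records under each reading**

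| Record | SAP 3.2, literal | SAP 3.2, by purpose | SAP 4.1 set |
|---|---|---|---|
| Device, bleed day 5, implant day 9 | Not counted (day −4 from implant) | Counted | Not counted (before time zero) |
| Control, bleed day 5 | Counted | Counted | Counted |
| Device Intent, bleed month 20 | Not counted (no start date) | Counted | Subject not in the set |

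**The plan's own figure.** The inputs in SAP 3.2.2 are 14% Device, 20% Control, two-sided alpha 5%, 20% attrition and N = 1600. Allocation is 1:1 (Protocol 11.6), so 800 per arm.

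- HR = ln(0.86)/ln(0.80) = 0.676.
- With exponential events and attrition, P(event) = λ/(λ+c) × (1 − exp(−3(λ+c))), where λ and c are the yearly event and attrition hazards. This gives 0.126 in Device and 0.180 in Control.
- Events = 800 × (0.126 + 0.180) ≈ 244.7.
- Schoenfeld power = Φ(√(244.7/4) × 0.392 − 1.96) = 86.5%. Freedman's formula gives 85.7%.

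The stated 86.4% reproduces. The issue lies in the endpoint definition and not in the sample-size arithmetic.

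**Pre-implant gap.** At a constant hazard, h = −ln(0.80)/1095 = 0.000204 per day, and events lost in g days = 800 × (1 − exp(−h × g)).

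- If every implant falls on day 10, Device loses 13 days (10 before, 3 after): 2.1 events.
- Control loses 3 days: 0.5 events.
- The one-sided excess is 10 days: 1.6 events (1.1 at a 14% rate).
- If both arms truly bleed at 20%, the chance of a false Device win from this window alone is about 3.0%, against 2.5%.

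This is an upper bound on implant timing. A subject whose early bleed is not counted may still have a later one counted.

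**Intent subjects, literal rule, all randomized analysed.** The documents give no Intent share f, so f is an assumption. So is a 20% bleeding rate in these subjects. If both arms truly bleed at 20%, the observed Device rate is 0.20 × (1 − f). Then:

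- HR = ln(1 − 0.20(1 − f))/ln(0.80)
- s = √(d/4) × (−ln HR), with d the expected events under 20% attrition
- P(false Device win) = Φ(s − 1.96)

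At f = 5%: HR = ln(0.81)/ln(0.80) = 0.944, d = 800 × (0.171 + 0.180) ≈ 280.8, s = 0.48, and Φ(−1.48) = 6.9%.

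| Intent share | Subjects | Bleeds lost, before attrition | False Device win |
|---|---|---|---|
| 0% | 0 | 0 | 2.5% |
| 1% | 8 | 1.6 | 3.1% |
| 3% | 24 | 4.8 | 4.7% |
| 5% | 40 | 8.0 | 6.9% |
| 10% | 80 | 16.0 | 16.1% |

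A log-rank simulation of 4,000 trials on the same assumptions gave 3.8%, 7.0% and 11.8% at shares of 2%, 5% and 8%, in line with the formula. With 20% attrition the observable loss at 5% is 40 × 0.18 = 7.2 bleeds.

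Under the planned effect (implanted subjects 14%, Intent 20%, f = 5%), the Device rate is 14.3% with Intent bleeds counted and 13.3% without. The difference from Control is 6.7 points instead of 5.7, an overstatement of about 18%. Power is 93.3% instead of 82.6%.

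**The case against.** A reader might infer that the plan excludes every Intent bleed, and so that the type I error is inflated. The documents do not support that. For a subject with neither date the rule is undefined, and no section says such bleeds fail it. The class being defined is non-procedural bleeding, and a subject with no procedure can have no other kind. Counting these bleeds is also the reading that best fits Protocol 10.2.3.1, Protocol 13.2.1 and SAP 3.2.3. This objection stands: the literal result is one way to program the rule and not a stated exclusion.

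Second, if SAP 4.1 governs, Intent subjects leave the risk set along with their bleeds. The bleeds are still lost, but the false-win figures above do not apply, because the denominator shrinks too. That also stands.

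Third, the Intent share and the 20% rate are assumptions. Protocol 10.2.3.1 says only that these subjects need not follow the Device medication requirements, not that they stay on anticoagulation. Protocol 13.1.1.2 includes subjects randomized but not treated in its 15% attrition, so some are expected, but it gives no separate number.

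Fourth, the pre-implant loss is close to immaterial. On size that is right. As a matter of wording, the asymmetry follows directly from SAP 3.2.

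**Conclusion.** The point holds as a gap and an asymmetry in the event rule. Two parts rest on the text alone: Device bleeds before implant are not counted while Control bleeds after day 3 are, and Intent subjects have no start date. The first costs at most about 1.6 events at a 20% rate.

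The second has no fixed size. The range from about 3% to 16%, against a nominal one-sided 2.5%, needs all four conditions: an Intent share of 1% to 10%, a 20% bleeding rate in those subjects, truly equal arms, and the literal rule applied to all randomized subjects. If their bleeds are counted, this part of the distortion disappears.

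The SAP does not choose between these readings, and SAP 3.2.3 and SAP 4.1 disagree on the analysis set. A required superiority endpoint should not be left to whoever programs it, so this should be settled before the analysis.

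**What to change.** In SAP 3.2 and Protocol 13.1.2, replace the rule with:

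> In both arms, bleeds within 3 days after randomization are not counted. In Device subjects with an implant or attempt, bleeds from the day of the procedure through 3 days after it are also procedural and not counted. All other bleeds, including those between day 3 and the procedure and all bleeds after day 3 in Device subjects with no implant or attempt, are non-procedural and are counted.

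Keep the first sentence. Without it, Device bleeds on the first 3 days before a later implant would count while the same Control bleeds would not.

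Reconcile SAP 4.1 with SAP 3.2.3 and Protocol 13.2.1 so that the primary safety analysis is on all randomized subjects. The treated-as-assigned set can remain as a sensitivity analysis. SAP 4.5 has the same gap: missing Device onset dates default to the implant date, with no rule for Intent subjects. Randomization would serve there too.

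The cost is a few sentences in an SAP amendment approved before the analysis, the matching protocol text, and a small programming change. No new data are needed: all bleeding events are reportable (Protocol 21.1) and the events committee adjudicates from randomization (Protocol 23.3). The downside for the sponsor is that the Device bleeding rate may be slightly less favourable.
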